3 STUDY FLOW CHART

	Pre-Rx 'Screening Phase' (duration	Baseline	Rx Phase 1		Rx Phase 2		
	= 15 days)	Day 0 +/-7	Day 30 +/-7	Day 90 +/-14	Day 120 +/-14	Day 180 +/-14	Day 360 +/-14
Enrolment Period	1 year						
Medical History**	X	X	X	X	X	X	X
Concomitant Medication(s)	X	X	X	X	X	X	X
Vital Signs	X	X	X	X	X	X	X
Physical Examination	X	X	X	X	X	X	X
ASRS(*)	X	X	X	X	X	X	X
IRLS(*)	X	X	X	X	X	X	X
RLS-QOL(*)		X	X	X	X	X	X
MOS-SS(+*)		X	X	X	X	X	X
CBC and differential, CMP	X		X				X
Monitoring & Recording of Adverse Events		X	X	X	X	X	X
Urine pregnancy analysis	X	X	X	X	X	X	X
Urine sample collection (drug screen)	X						
Serum pregnancy analysis Serum Ferritin Level	TBD	TBD	TBD	TBD	TBD	TBD	TBD

Rx Phase 1 (Day 0-90) = Stable DA + Horizant

Rx Phase 2 (Day 120-360) = DA taper/Horizant only

- + = Subjects will also be requested to keep a sleep diary.
- * = See attachments.
- ** = Medical history includes Interval history between clinic visits.

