Abrupt withdrawal of DA agent can be potentially dangerous due to DA withdrawal symptoms including life-threatening Neuroleptic Malignant Syndrome. Therefore, Rx Phase 1 and Rx Phase are designed to help improve subject tolerability.

Therefore, during Rx Phase 1, Horizant (600 mg oral once daily at 5 pm) will be added on as an adjunct to all subjects' along with stable dose of their current dopaminergic (DA) agent and both medications will be continued for a total period of 90 days from day 0 to day 90.

At the 90th day follow-up visit, with initiation of Rx Phase 2, all subjects will be tapered off (by 50% reduction in dose each week) of their current dopaminergic agent while maintaining the same dose of Horizant and will be on Horizant monotherapy. All subjects will be followed for additional three follow up clinic visits (days 120, 180, 360).

During this period all subjects will be monitored for symptoms of dopamine withdrawal or worsening of RLS or emergence of other symptoms which will be managed clinically by physicians. All subjects will continue to be on Horizant for the entire duration of this study with close follow up. Of note, if deemed appropriate for reasons related to safety, tolerability, and continuation of the study, the PI, at his discretion, may modify the tapering schedule of the DA although every attempt will be made to adhere to the protocol specified schedule of DA tapering.

During each clinic visit all subjects will undergo careful evaluations (by a physician) that will include: medical history such as appearance of any new health problems, any new symptoms/adverse events between clinic visits, concomitant medication(s) history (medication reconciliation), physical examination with assessment of vital signs, ASRS, IRLS, RLS-QOL, and MOS-SS.

All subjects will undergo laboratory testing (CBC with Diff and CMP) during screening, on day 30 and day 360 (final clinic visit). In addition, urine sample will be collected at screen visit for illegal drug testing. Additional hematology and urine sample analysis for illegal drug will be performed as needed at the discretion of the investigators if an adverse event is reported by a subject. Serum Ferritin level will be performed as needed at the discretion of the investigators.

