Urine pregnancy screening is required for all females of childbearing potential at screen and each clinical visits, if positive, serum pregnancy test will be performed. Female subjects who have undergone surgical sterilization, who are post-menopausal (defined as age >50 and >1 year of amenorrhea), who have medically documented ovarian failure (defined as age <50 with serum estradiol and follicle-stimulating hormone [FSH] levels within the institutional postmenopausal range and a negative serum or urine β HCG) do not need to undergo pregnancy screening.

At study completion, appropriate statistical analysis will be performed to evaluate the outcomes. We plan to publish the findings and results of this study.

Study Population:

Primary RLS patients who developed augmentation on DA therapy and score of 5 to 15 on ASRS scale.

We plan to recruit 50 patients; male and female, age 18-85 years.

Recruitment site is University of Missouri-Columbia. We may use advertisement(s) in the local media to recruit subjects.

Outcome Parameters/Evaluation:

The Primary outcome parameter:

- 1) A reduction in the Augmentation Severity Rating Scale (ASRS)
- 2) Improvement in the International Restless Legs Syndrome-Rating Scale (IRLS)
- 3) Improvement in the Restless Legs Syndrome-Quality of Life (RLS-QOL)
- 4) Improvement in the Medical Outcome Study-Sleep Scale (MOS-SS)

The Secondary outcome parameters:

- 1) A reduction in the Augmentation Severity Rating Scale (ASRS)
- 2) Improvement in the International Restless Legs Syndrome-Rating Scale (IRLS)
- 3) Improvement in the Restless Legs Syndrome-Quality of Life (RLS-QOL)
- 4) Improvement in the Medical Outcome Study-Sleep Scale (MOS-SS)

Treatment Group: This is a Single Arm study. All subjects will receive Horizant 600 mg once daily.

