5. BACKGROUND

5.1 Study Rationale:

RLS is common condition that is usually treated with dopaminergic medications. Augmentation is the main complication during long-term DA treatment of RLS. It was first described in 1996 with overall increase in severity of RLS symptoms typically more severe than pre-dopaminergic therapy with earlier occurrence of symptoms and involvement of previously uninvolved extremities. It can be a very devastating experience in some patients. Augmentation is reported in up to 82% of people taking levodopa (Allen RP, Earley CJ. Augmentation of the restless legs syndrome with carbidopa/levodopa. Sleep 1996;19:205-13)

Features of Augmentation include earlier onset of RLS symptoms, increased severity of symptoms, reduced time before symptoms begin when resting, spread of symptoms to previously uninvolved body parts, and reduced effectiveness of medications including longer time before medication begins to work and less ability to decrease symptoms.

Augmentation severity can be assessed by a validated scale, ASRS, in these patients.

Management of Augmentation has not been studied in clinical trials. Presently, there is no approved medication (by FDA) to treat augmentation. In addition, currently, there are no specific practice guidelines as to how to treat augmentation. 'More research is needed to identify the optimal approach for treating augmentation once it develops. Sudden withdrawal of the offending dopaminergic drug does not appear to be a well-tolerated strategy' (Kurlan. Journal of Parkinsonism & Restless Legs Syndrome Vol 3, 49-52, 2013).

Pubmed search (conducted in Jan 2015, with key words "Horizant, Augmentation") revealed several articles (see attachments) suggesting that Horizant is the only FDA approved Nondopaminergic drug used in the treatment of RLS, with predictable bioavailability, acceptable safety profile and with any reports of augmentation. Therefore, we suggest that Horizant may be a best-suited drug to treat augmentation in RLS patients. Thus, we propose to conduct a clinical drug trial to examine Horizant in RLS patients who developed augmentation.

Abrupt withdrawal of DA agent can be potentially dangerous due to DA withdrawal symptoms including life-threatening Neuroleptic Malignant Syndrome. Therefore, to improve subject tolerability and minimize DA withdrawal, we have designed this clinical trial into 2 phases: Rx Phase 1 and Rx Phase 2 (described below)

6. Objectives:

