The Primary objective: is to evaluate the efficacy of Dopamine combined therapy with addition of Horizant (600mg, oral, once daily) for 90 days in the treatment of Augmentation.

The Secondary objectives: is to evaluate the efficacy of Horizant (600 mg, oral, once daily) alone with Dopaminergic (DA) taper for up to 270 days in the treatment of Augmentation.

6.1 Study Design:

This is an Open label Single arm study. The purpose of the study is to demonstrate the efficacy of Horizant in patients with RLS who exhibit augmentation while on Dopaminergic therapy. Adult patients (age 18-85 years) with diagnosis of primary RLS (diagnosed by study investigators) with augmentation on dopaminergic therapy will be screened for participation in the study. RLS diagnosis will be made by the study investigators using International RLS study group criteria. Patients with augmentation on dopaminergic therapy as defined by NIH 2007 (refer to attachment) with ASRS of 5 to 15 will be offered to participate in the study. Inclusion and exclusion criteria are listed below. The study will be performed after approval of the Institutional Review Board of the University of Missouri.

A total of 50 subjects will be entered into the study over a period of 1 year. Written consent will be obtained from all patients. After pre-participation evaluation for eligibility, subjects will be selected and enrolled in the study and followed for a total of 6 follow up visits (Days 0, 30, 90, 120, 180, 360). Subjects Enrollment period will last up to 12 months. The total duration of study is 36 months.

There is no report of Augmentation due to Horizant use in the literature to this date. Therefore, initially Horizant (600 mg oral once daily at 5 pm) will be added on as an adjunct to all subjects' along with stable dose of their current dopaminergic (DA) agent and both medications will be continued for a total period of 90 days from day 0 to day 90.

At the 90th day follow-up visit, while maintaining the same dose of Horizant, all subjects will be tapered off (by 50% reduction in dose each week) of their current dopaminergic agent. Subsequently all subjects will be followed for additional three follow up clinic visits (days 120, 180, 360). During this period all subjects will be monitored for symptoms of dopamine withdrawal or worsening of RLS or emergence of other symptoms which will be

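### In Phase 2 the dopaminergic agent is removed, Horizant is unchanged and there is no comparator, so a fall in ASRS at Days 120 to 360 cannot by itself show efficacy of Horizant alone

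*Protocol*

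**What the plan says.** Section 5.1 (Study Rationale) presents augmentation as arising from dopaminergic treatment: "Augmentation is the main complication during long-term DA treatment of RLS". It also quotes a cited source that calls the DA the cause of the trouble: "Sudden withdrawal of the offending dopaminergic drug does not appear to be a well-tolerated strategy". The same section names ASRS as the scale for the severity of augmentation.

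Section 4 (Summary, Study Design) has all subjects tapered off the DA from the Day 90 visit "while maintaining the same dose of Horizant and will be on Horizant monotherapy". The flow chart in section 3 gives the same picture: "Rx Phase 2 (Day 120-360) = DA taper/Horizant only". Follow-up visits are at Days 120, 180 and 360.

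The secondary objective, in sections 4 and 6, evaluates Horizant "alone with Dopaminergic (DA) taper for up to 270 days in the treatment of Augmentation". The secondary outcomes in section 4 are the same four scales, in the same order, as the primary outcomes. The first is "A reduction in the Augmentation Severity Rating Scale (ASRS"; IRLS, RLS-QOL and MOS-SS follow. All four are rated at every Phase 2 visit (section 3, section 10.1). The design is open label with a single arm (section 6.1).

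**The concern.** The secondary objective asks what Horizant alone does for augmentation, but Horizant is the one thing that does not change in Phase 2. What changes is the DA, which the rationale treats as the source of augmentation. If ASRS falls after Day 90, removal of the DA is a ready explanation, and nothing in the design separates it from a Horizant effect.

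There is a second difficulty. ASRS is introduced as a grading of augmentation in patients on a DA. What a given score means once the DA is gone is not explained.

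At stake is the Phase 2 conclusion. As worded, a lower ASRS at Days 120 to 360 could be reported as Horizant alone treating augmentation. The protocol itself anticipates possible worsening of RLS in this period, and whether RLS stays controlled without the DA is a separate question that ASRS alone does not settle.

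**Working it through.** The protocol derives no figure on this point: the 50 subjects in section 7.1 rest on expected recruitment. There is nothing to reproduce, so the check is mainly a comparison of sections.

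**1. What changes, by reference visit.** The outcome list does not name a reference visit. Neither obvious choice isolates Horizant.

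| Reference | What differs at Days 120 to 360 |
|---|---|
| Day 0 | Horizant added, DA removed, time elapsed |
| Day 90 | DA removed, time elapsed; Horizant the same |

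Measured from Day 90, the change contains no change in Horizant at all. Measured from Day 0, the Horizant and DA effects are mixed.

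**2. How far the DA is removed at each visit.** Assume that the weekly 50% reduction halves the current dose. After k cuts the remaining fraction is 0.5^k. The lower k below puts the first cut a week after the Day 90 visit, and the higher k puts it at that visit.
- Nominal Day 120, 30 days after Day 90: k = 4 or 5, leaving 6.25% or 3.1%.
- Shortest gap within the ±14-day windows, Day 104 to Day 106 (2 days): k = 0 or 1, leaving 100% or 50%.
- Longest gap, Day 76 to Day 134 (58 days): k = 8 or 9, leaving 0.4% or 0.2%.
- Day 180 at its earliest, Day 104 to Day 166 (62 days): k = 8 or 9, again 0.4% or 0.2%.

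If each cut is instead half of the starting dose, two cuts reach zero. On schedule, then, most Phase 2 ratings are made essentially off the DA. DA exposure at the Day 120 visit can still vary widely between subjects, even before any discretionary change to the taper.

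**3. What the listed features allow.** Section 5.1 gives: "Features of Augmentation include earlier onset of RLS symptoms, increased severity of symptoms, reduced time before symptoms begin when resting", then spread to other body parts and reduced effect of medication. Only the last refers to medication. The others are RLS symptoms that could ease, persist or worsen after the DA stops. The text therefore does not fix the direction of ASRS after the taper.

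**4. Illustration of scale (assumed inputs).** Take a one-sample t test on the change, two-sided 5%, and let DA removal alone shift mean ASRS by d SDs of the change, with no Horizant effect. The smallest significant mean change at n = 50 is t(0.975, 49)/√50 = 0.284 SD. The probability of significance comes from the noncentral t distribution with noncentrality d√n:

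| Assumed d | n = 50 | n = 40 |
|---|---|---|
| 0.2 | 0.28 | 0.24 |
| 0.3 | 0.55 | 0.46 |
| 0.4 | 0.79 | 0.69 |
| 0.5 | 0.93 | 0.87 |

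The values of d, the 5% level and n = 40 are assumptions. The same table would apply to any scale. It shows only that a moderate non-Horizant shift would often be read as a positive result.

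**The case against.** The strongest reply is that ASRS fits the objective as written. That objective concerns treatment of augmentation, names the taper as part of what is evaluated, and uses a scale the protocol calls validated for that purpose. The single-arm design is openly stated, and the attribution problem applies to IRLS, RLS-QOL and MOS-SS as well. The outcome list is unranked and carries no Phase 2 label, so being first confers no formal status. IRLS is already on the list and rated at every Phase 2 visit. All of this stands. It limits the point to how the Phase 2 result is attributed and how ASRS is read off the DA. It does not remove it, because the objective still credits Horizant alone and nothing in the protocol prevents a Phase 2 claim resting on ASRS while IRLS shows no benefit.

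A reader might infer more than the documents support:
- **That ASRS must fall once the DA is gone.** The ASRS items are in an attachment not shown. The working definition of augmentation is external too: "Patients with augmentation on dopaminergic therapy as defined by NIH 2007 (refer to attachment) with ASRS of 5 to 15". The sentence in section 5.1 is background description, and most listed features could persist or worsen.
- **That a subject with worsening RLS would still score well on ASRS.** Greater symptom severity is itself a listed feature of augmentation, so without the items this is conjecture.
- **That a tapered control arm would not help.** A fall shared by both arms cancels in the between-arm difference, so such a comparison would address attribution.
- **That Phase 2 fails to measure RLS control.** It does measure it, through IRLS.

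**Conclusion.** The point holds as one of confounding and interpretation. In Phase 2 the only planned treatment change is removal of the drug that the rationale treats as the source of augmentation, with Horizant constant and no comparator. A post-taper fall in ASRS cannot be separated from DA removal, and its meaning off the DA is unclear. It cannot by itself support efficacy of Horizant alone or continued control of RLS. All three Phase 2 visits are affected.

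The size cannot be derived from the protocol, which gives no expected ASRS change, SD or dropout rate. The probabilities above are illustration and not evidence about ASRS. The conclusion assumes that the secondary outcome list serves the secondary objective, which the protocol implies without stating, and that the taper is broadly carried out. The investigator may modify the taper, so removal may be incomplete in some subjects.

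**What to change.** 1. In sections 4 and 6, reword the secondary objective so that it evaluates the strategy of DA taper plus Horizant, including RLS control after DA removal, and does not credit the result to Horizant alone.
2. In the secondary outcomes in section 4, name IRLS, with a stated reference visit, as the Phase 2 measure of RLS control at Days 120, 180 and 360.
3. Report ASRS after Day 90 beside IRLS, labelled as measured after the DA taper and shown with the subject's DA status at that visit. Do not use it alone to support a Phase 2 efficacy claim.

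The cost is protocol wording. All four scales are already collected at each Phase 2 visit, and DA status can come from the medication reconciliation already done at each visit (section 8.13). The small loss is that ASRS no longer carries a stand-alone Phase 2 claim. IRLS has no comparator either, so the Phase 2 conclusion stays at the level of the strategy.

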8. STUDY MEDICATION, DESCRIPTION, AND ALLOCATION

Study drug is not to be used beyond the initial expiration date on the drug packaging.

8.1 Horizant Stability & Storage

HORIZANT Extended-Release Tablets containing 600 mg of gabapentin enacarbil are white to off-white, with occasional black/grey spots, oval-shaped tablets debossed with "GS LFG". They are supplied as follows:

600 mg: NDC 53451-0101-1: Bottles of 30

Store at 25°C (77°F); excursions permitted 15° to 30°C (59° to 86°F) [see USP Controlled Room

- 8.2 Other Study Drug Generic Name (Brand Name®) Not applicable
- **8.3 Randomization Procedure**: Not Applicable.
- **8.4 Blinding Procedures** Not Applicable
- 8.5 Drug Accountability:

The study site must maintain accurate records demonstrating dates and amount of study drug received, to whom they are dispensed (subject-by-subject accounting), and accounts of any study drug accidentally or deliberately destroyed. If drug is provided by XenoPort, the investigator must return all unused vials of study drug to XenoPort Inc. pursuant to instructions (unless agreed otherwise by XenoPort Inc.).

8.6 Treatment Schedule: as per study design.

8.7 Modification of Treatment Schedule for Horizant:

If deemed necessary for individual subject's safety, it is at the discretion of the treating physician to modify the schedule of dosage of 600 mg according to the approved package insert; however, every attempt should be made to maintain the scheduled study dosing.

8.8 Modification of Treatment Schedule for Other Study Drug: as per protocol.

8.9 Discontinuation of Subjects from Investigational Treatment or from the Study

Subjects must be withdrawn from the study for the following reasons:

- 1. If a subject develops significant adverse effect(s) after addition of Horizant or subject experiences significant DA withdrawal side effects as judge by the investigator.
- 2. If a subject is diagnosed to have a new medical condition while participating in the study that would fall into exclusion criteria (6.3) or if management of a newly diagnosed acute medical problem requires termination of the study medication.
- 3. If a subject becomes pregnant.
- 4. If a subject is deceased.
- 5. XenoPort Inc. may terminate this study, after consultation with investigators, at any time.

8.10 Discontinuation of Study Drug:

The reasons for discontinuation of the study drug must be recorded in the subject's case report form (CRF).

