- We will instruct you on how to discontinue any medications not allowed while you are in the study. Without your regular medications, your medical conditions or symptoms may get worse however, we will check with the doctor that prescribed the medication to make sure that it is safe for you to stop taking it. You might not be able to drive or operate machinery. If your medical conditions or symptoms do get worse, please call the study doctor at the phone number provided in this consent form.
- We will make an appointment for you to return for Visit 2 (baseline visit), within the next 15 days or less.

Visit 2 (day 0+/-7), visit 3 (day 30+/-7), visit 4 (day 90+/-14), visit 5 (day 120+/-14), visit 6 (day 180+/-14) and visit 7 (day 360+/-14) will have the following tests and procedures except that visit 2, 4, 5 and 6 will not have blood sample collection.

- Medical history: We will ask about your health and any illnesses and any changes in medicines you are taking or have taken since last visit.
- We will ask you about your current and prior Augmentation treatment, symptoms, your usual bedtime and awakening times.
- You and the staff will complete assessments on how you are feeling and if you have any thoughts about harming yourself.
- Physical examination: You will have a full physical examination including neurological exam, height and weight.

- Vital signs: You will have your temperature, heart rate, blood pressure, temperature and breathing rate collected.
- Blood testing: We will collect blood samples (2 teaspoon or~10ml) for lab tests including hematology. Additional blood sample (~1/4 of teaspoon or 1.25ml) will be collected if you are a woman and your urine pregnancy test turn positive.
- Urine testing: You will collect a sample of urine for pregnancy testing.
- Augmentation severity rating scale (ASRS) 3 item questionnaire to evaluate the severity of your augmentation symptom.
- International restless legs syndrome-rating scale (IRLS) a way to measure severity of your symptoms.
- Restless legs syndrome-quality of life (RLS-QOL) a way to measure improvement in quality of your life.
- Medical outcome study-sleep scale (MOS-SS) a way to assess your sleep.

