11 ADVERSE EVENTS/SERIOUS ADVERSE EVENTS – DEFINITION & REPORTING

At the signing of the informed consent form, each subject will be given the names and telephone numbers of investigational site personnel for reporting adverse events and medical emergencies.

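### Section 8.9 ties significant intolerance to leaving the study, and the protocol requires no efficacy rating because of that exit or after it

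*Protocol*

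**What the plan says.** The heading of section 8.9 separates discontinuing treatment from discontinuing the study, but its operative sentence covers only the second: "Subjects must be withdrawn from the study for the following reasons". The first reason listed is "If a subject develops significant adverse effect(s) after addition of Horizant or subject experiences significant DA withdrawal side effects as judge by the investigator".

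On what is collected at that point, section 8.10 says "The reasons for discontinuation of the study drug must be recorded" and asks for nothing more. The visit list under Study Procedure in section 6.1 runs from screening through Days 0 and 30, and then "visit 4 (day 90+/-14), visit 5 (day 120+/-14), visit 6 (day 180+/-14) and visit 7 (day 360+/-14) will have the following tests and procedures". Neither it nor the section 3 flow chart has an early-discontinuation visit. Sections 9.3 and 10.1 attach ASRS, IRLS, RLS-QOL and MOS-SS to each clinic visit. The only follow-up stated after a subject leaves is in section 11.1.2, for a serious adverse event that has not resolved.

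Other text softens the route to exit. In Phase 2, subjects are "monitored for symptoms of dopamine withdrawal or worsening of RLS or emergence of other symptoms which will be managed clinically by physicians". The principal investigator "may modify the tapering schedule of the DA although every attempt will be made to adhere to the protocol specified schedule of DA tapering" (section 4, repeated in 6.1). For Horizant, section 8.7 says that "it is at the discretion of the treating physician to modify the schedule of dosage of 600 mg according to the approved package insert".

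**The concern.** Stopping a drug and leaving a study are different events. Section 8.9 merges them for the subjects who tolerate the regimen worst. The primary objective concerns 90 days of Horizant added to the dopaminergic agent (DA). The secondary objective concerns Horizant alone with the DA tapered. Failing to tolerate Horizant, or the taper, is an unfavourable result of the strategy under test, yet the rule ends data collection for exactly those subjects.

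All outcomes listed in section 4 are reductions or improvements in scale scores. The trial is open label with a single arm, so there is no control group against which to judge selective loss. An analysis plan can choose how to handle missing scores, but it cannot recover ratings that were never taken. That makes this a matter for the protocol.

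**Working it through.** The protocol states no withdrawal rate and gives no figure on this point to reproduce. The check is a reading of the relevant sections side by side, followed by a count of what one exit costs.

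**Step 1: does exit follow from these events?** Yes, once the investigator judges them significant (8.9, reason 1). The clinical management, taper changes and dose changes in sections 4, 6.1 and 8.7 may keep some subjects from reaching that point. They provide no rating for those who do.

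**Step 2: is there a rating at exit?** It depends on where the decision is made.
- At a clinic visit: yes, through 9.3 and 10.1, which are not limited to scheduled visits.
- Outside a visit: none is required. Section 11 says "each subject will be given the names and telephone numbers of investigational site personnel for reporting adverse events and medical emergencies", so a report can arrive between visits. That withdrawal could then be decided without a visit is an inference. The protocol neither provides for it nor excludes it.

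**Step 3: is there a rating after exit?** None is required. The safety follow-up in 11.1.2 does not include the efficacy scales. The statements in section 4 that all subjects attend Days 120, 180 and 360 describe the planned schedule and do not override a mandatory withdrawal.

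**Step 4: scheduled scores lost per exit.** Inputs: post-baseline visits at Days 30, 90, 120, 180 and 360, with four scales at each (section 3). Scores lost = remaining visits × 4.

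| Exit falls between | Scheduled visits lost | Scores lost, of 20 | Consequence |
|---|---|---|---|
| Day 0 and 30 | 5 | 5 × 4 = 20 | no scheduled post-baseline score |
| Day 30 and 90 | 4 | 4 × 4 = 16 | Day 90 scores lost |
| Day 90 and 120 | 3 | 3 × 4 = 12 | all scheduled Phase 2 scores lost |
| Day 120 and 180 | 2 | 2 × 4 = 8 | Days 180 and 360 lost |
| Day 180 and 360 | 1 | 1 × 4 = 4 | Day 360 lost |

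An unscheduled clinic visit at exit would add four scores to any row, but would not replace the later scheduled ones. Each exit before Day 90 removes 1/50 = 2% of the planned Day 90 data.

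**Step 5: how the loss would act on an observed-score mean.** Let d be the share without a score, and let the gap be the mean improvement in those observed minus the mean improvement in those who exit. The observed mean then exceeds the mean for all enrolled by d × gap. Neither input is in the protocol. Purely as assumed values for ASRS:
- gap of 2 points: d = 10%, 20%, 30% gives 0.10 × 2 = 0.2, 0.20 × 2 = 0.4, 0.30 × 2 = 0.6 points;
- gap of 4 points: the same shares give 0.4, 0.8 and 1.2 points;
- gap of 0: no bias at any d.

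These values show direction and scaling. They are not an estimate for this trial.

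**The case against.** The strongest reply is that the protocol already covers most of this. Exit under reason 1 needs the investigator's judgement, symptoms are managed by physicians, and extra laboratory tests may be done when an adverse event is reported. All of this suggests attendance at the clinic, where 9.3 and 10.1 call for all four scales. Taper changes are allowed partly so that subjects can continue in the study. The handling of exits in the analysis, for example as failures in a responder analysis, is commonly left to the analysis plan. Ratings after exit would also partly reflect resumed DA or other therapy, so they do not address either objective directly.

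Much of this stands. A reader might infer from 8.9 and 8.10 that nobody who exits is rated at that point; 9.3 and 10.1 do not support that for an exit decided at a clinic visit. A reader might also infer that every withdrawal symptom or adverse effect forces exit; the provisions for clinical management and modification contradict this. It would likewise be too strong to say that results will be biased upward, because the protocol fixes no observed-case analysis and gives no rate or outcome for those who exit.

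The reply does not remove the core. No visit is made compulsory by exit, ratings stop afterwards, and a responder analysis would not restore scores on the listed scale outcomes.

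**Conclusion.** The point holds in a limited form and should be fixed. As written, 8.9 turns significant intolerance into departure from the study, with no visit or rating required on that account and none later. The loss is certain for scheduled scores after exit; for a rating at exit, it arises only when the decision is made outside a clinic visit.

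The size of any bias cannot be derived. It depends on the share who exit and on how they fare compared with those who stay. It is zero if they fare the same, and it favours benefit if they fare worse and the analysis uses observed scores. Nothing here shows the trial to be invalid. It is an avoidable loss of data, related to tolerance of the regimen, with a cheap remedy.

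**What to change.** Reword reason 1 of section 8.9 so that significant Horizant effects or significant DA-withdrawal effects stop Horizant or the taper, as appropriate, rather than study participation. Add an early-discontinuation column to the section 3 flow chart, with a matching entry in the visit list, for a visit held when treatment stops at which ASRS, IRLS, RLS-QOL and MOS-SS are completed. Leave the existing discretion to manage symptoms and to modify the taper or Horizant dosing as it is.

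Optionally, for subjects who consent, keep the remaining scheduled ratings, record the date of any return to DA or other RLS therapy, and treat those scores as supportive. The exit visit captures the subject's state when treatment stops; only this optional step would also yield Day 90 or Phase 2 scores.

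The cost is one reworded item, one flow-chart column and visit-list entry, one consent sentence and one extra visit per affected subject, using scales already in the study. If the optional ratings are kept, there are also a few off-drug visits, with later scores that partly reflect other therapy.
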